## **Project Summary**

Ptosis (eye lid drooping) can be corrected surgically via a procedure called Fasanella servat. As eyelid tissue is cut and existing edges sutured back together, the sutures can cause some irritation to the eye. Bandage contact lenses are used with the idea that it will protect the cornea by providing a protective layer from the sutures (Fontana, 1978). A study conducted by Awan *et al.* suggests that soft contact lenses may be a beneficial choice in surgeries involving the upper eyelid (Awan, 2009). To truly see any benefits in patients, studying the effects of bandage contact lenses in patients with ptosis surgery is important. Patients who require ptosis surgery on both eyes will be part of the study and one eye will be randomized to receive the bandage contact lens and the other eye will not. Pain/discomfort and blurred vision will be compared between the 2 eyes and the results will help us determine if the use of bandage contact lenses is warranted in ptosis eye surgery. If the lens is found to be unneeded, this can provide significant healthcare cost savings and prevent unnecessary resource utilization. Moreover in terms of the patient experience, if the lens is unneeded, this can provide a more comfortable recovery period (no hassles with keeping the lens in place) and any unnecessary complications by having a lens on the eye (i.e. blurred vision, foreign body sensation, etc.). Bandage contact lenses have been demonstrated to have reduced discomfort; however, patients had a preference not to wear them during the later parts of their recovery time as they did not experience much in terms of blurred vision and discomfort (Ahmed et al, 2001). Moreover, in a study by Shimazi *et al.* with corneal transplantation, it was concluded that no significant benefits were observed through the use of bandage contact lenses in their patients (Shimazi et al, 2016). Based on the above, it is hypothesized that the bandage contact lenses will not have a major impact on the pain/discomfort that the patient experiences and likely will not need to be routinely used.

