## **Methods**

**Participants:** The study population will include patients who have bilateral ptosis (drooping eyelids) and will require surgery to correct this, patients in this study will have no other eye related pathologies. In general, patients are older than 50 years old and from any demographic.

**Design and Procedure:** In this randomized control trial, 30 patients requiring surgery (Fasanella Servat procedure) with bilateral ptosis will have one eye randomized to receive a bandage contact lens whereas the other eye will not after their surgery. Participants will have a random number assigned in order to anonymize data and protect patient identity. We will place a contact lens on both eyes and immediately take it off from one (this will be the sham lens eye). Randomization of the lens placement will be determined by a flip of a coin (heads – keep lens on right eye. Tails – keep lens on left eye). Investigator will randomly generate for each patient whether the contact lens will be kept on right or left eye, sham contact lens will be placed on other eye, placing it and immediately removing it. Therefore, the patient will not know which eye has a lens. Follow up will occur in one week after their surgery where the outcomes will be obtained through questionnaires. Upon 1 week follow up, the person administering the questionnaire is also blinded as they will not know which eye was randomized to have the lens placed. The primary outcome that will be obtained during the study is the patient's pain/discomfort. This will be obtained using the Eye Sensations Scale where the patient can select a box from None, Mild, Moderate, Severe, to Extreme. The secondary outcome that will be obtained is to determine if the patient has experienced blurry vision. This will be measured using one question from the Ocular Surface Disease Index (OSDI), with a scale from 0 (none of the time) to 4 (all of the time).

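### A finding that the lens is unneeded would be wider than the evidence, because no corneal finding or clinician-recorded complication is collected by eye

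*Combined protocol and SAP*

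**What the plan says.** The Project Summary states the rationale for the lens, namely the idea that "it will protect the cornea by providing a protective layer from the sutures". One sentence later in that section then names both the evidence and the decision. Its first half reads "Pain/discomfort and blurred vision will be compared between the 2 eyes"; its second half says that "the results will help us determine if the use of bandage contact lenses is warranted in ptosis eye surgery". The section goes on to what would follow: "If the lens is found to be unneeded, this can provide significant healthcare cost savings". It closes with a hypothesis of no major effect on pain/discomfort, from which it expects that the lens "likely will not need to be routinely used".

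Methods (Design and Procedure) sets the outcomes: "The primary outcome that will be obtained during the study is the patient's pain/discomfort", rated on the five-level Eye Sensations Scale. Blurry vision is secondary, from a single OSDI item scored 0 to 4. There is one follow-up, at one week, with outcomes taken by questionnaire, and the person giving the questionnaire is masked to allocation. No eye examination is described.

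Statistics and Analysis plans a paired t-test for the pain score and a McNemar test for a categorical outcome that it does not name. Ethics holds that participation adds no risk and that the surgical risks do not differ between the two treatments. It describes no recording of complications.

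**The concern.** The rationale for the lens is a property of the cornea; the evidence is two patient ratings. A result of little difference in comfort is what the plan expects, and the Project Summary links such a result to not using the lens routinely and to cost savings. A reader would take that to mean the lens gives no worthwhile protection, which the planned data cannot show. An abrasion diagnosed in a control eye before the visit would appear, at most, as a higher pain or blur score, with no diagnosis attached. An event with few symptoms at one week, or one that had already healed, could leave no trace. The Ethics section's assumption of equal risk would also go unchecked. Unless these events are recorded as they become known, they may be hard to recover after the six-month study.

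**Working it through.** **1. Purpose, decision and data side by side.**

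| Element | Section | Content |
|---|---|---|
| Rationale for the lens | Project Summary | Shielding the cornea from sutures |
| Decision to be informed | Project Summary | Whether the lens is warranted or unneeded |
| Lens complications named | Project Summary | Blurred vision and foreign body sensation, as examples |
| Outcomes | Methods | Pain/discomfort; one blur item |
| Method and time | Methods | Questionnaire at one week |
| Corneal finding, infection, suture problem or unscheduled visit, by eye | All sections | None stated |

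Of the two named complications, blur is compared by eye. Foreign body sensation has no item of its own, though the pain/discomfort scale may partly capture it.

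**2. The plan's own figure.** Inputs from Statistics and Analysis: difference 1, SD 1.6, power 90%, alpha 0.05 (two-sided assumed), 30 patients. Taking 1.6 as the SD of the within-patient difference:

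- Normal approximation: n = (1.6 × (1.960 + 1.282) / 1)² = 26.9, so 27.
- Exact paired t: n = 29; power at n = 30 is 91.1%.

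The 30 therefore reproduces on that reading, and it is sized for pain alone. The present point does not depend on it, except that 30 fixes how much a corneal count could show.

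**3. Chance that an event occurs to be recorded.** With true rate p per control eye, P(at least one in 30) = 1 − (1 − p)³⁰. The rates are assumptions, since the documents give none:

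- p = 2%: 1 − 0.545 = 45%
- p = 5%: 1 − 0.215 = 78.5%, about 79%
- p = 10%: 1 − 0.042 = 95.8%, about 96%

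These take p as the rate still detectable, or already diagnosed, at one week. If only half of events at 5% or 10% were picked up, p becomes 2.5% or 5% and the chances fall to 1 − 0.975³⁰ = 53% and to 79%.

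**4. What zero events would exclude.** With 0 of 30, the one-sided 95% upper bound is 1 − 0.05^(1/30) = 9.5%. The two-sided exact 95% upper limit is 1 − 0.025^(1/30) = 11.6%.

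**5. Whether a test would help.** In the exact two-sided McNemar test, m discordant pairs all in one direction give p = 2 × 0.5^m. Five pairs give 0.0625 and six give 0.031, so six are needed. With essentially no discordance the other way, power with 30 pairs is about 0.3%, 7%, 57% and 92% when 5%, 10%, 20% and 30% of patients have the event only in the control eye. With 5% discordance the other way, it is 24% at 20% and 57% at 30%. A test would miss all but very large differences, so description is the suitable form of report.

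**The case against.** The strongest reply is that the plan is a comfort trial and says so. The Project Summary opens with sutures irritating the eye, and pain/discomfort measures irritation directly. The sentence about whether the lens is warranted begins by naming the two outcomes and says only that the results will help. The hypothesis is tied to pain/discomfort and hedged. Blur is both a named lens complication and an outcome compared by eye, and a symptomatic abrasion could raise the pain score.

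Most of that stands. A reader might infer that no complication of any kind is captured by eye, or that the plan commits to abandoning the lens on comfort alone. The documents support neither. The gap is confined to corneal findings and clinician-recorded complications. It remains a gap because the plan never offers pain or blur as a stand-in for corneal protection, and because the words warranted and unneeded carry no limit to comfort.

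A second reply concerns feasibility. A reader might assume that the eye is examined at one week, so that findings need only be written down. The documents do not say so, and if no examination takes place, recording epithelial defects at the visit would add a procedure. Masking matters too: the time of lens removal is not stated, and anyone examining an eye with the lens still in place would see the allocation. Both objections limit the remedy. Neither applies to recording what has already been diagnosed, provided it is kept away from the masked administrator.

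A third reply is that 30 patients are too few to settle safety. That is correct, and it is why no test is proposed. It is not a reason to leave known events unrecorded.

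**Conclusion.** The point holds as a mismatch between the reach of the conclusion and the evidence. The planned data can support a statement about pain/discomfort and blurred vision at one week. They cannot support one about corneal protection, and so cannot by themselves support calling the lens unneeded.

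The size of what would be missed depends entirely on assumed event rates. Events in control eyes would be likely to occur at 5% to 10%, but at 2% it is closer to an even chance. Even with recording, rates below about 10% could not be ruled out.

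A reader might go further and infer that control eyes are being harmed, or that the trial is unsafe. The documents give no corneal event rate and no evidence of harm, so that does not follow. The comparison of comfort and blur, the primary analysis and the sample size are untouched by this point. The change is worth making before enrolment because it is cheap and the information may not be recoverable later.

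**What to change.** 1. **Narrow the conclusion.** Reword the Project Summary so that it covers pain/discomfort and blurred vision at one week. State that corneal protection was not tested, unless corneal findings are reported alongside.
2. **Record known events by eye.** At the existing follow-up, note for each eye any complication diagnosed since surgery (corneal abrasion or epithelial defect, infection, suture-related problem) and any unscheduled eye visit. Use a form separate from the questionnaire and completed after it, so that the administrator stays masked. Add corneal examination findings only if the eye is already examined at that visit; the sponsor should confirm whether it is.
3. **Report descriptively.** Give counts by eye with exact 95% confidence intervals and no formal test.

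The cost is a short form, one table and a narrower claim. Randomisation, primary outcome, primary analysis and sample size do not change. The report should say that 30 eyes per condition cannot exclude uncommon harm.

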## **Methods**

**Participants:** The study population will include patients who have bilateral ptosis (drooping eyelids) and will require surgery to correct this, patients in this study will have no other eye related pathologies. In general, patients are older than 50 years old and from any demographic.

**Design and Procedure:** In this randomized control trial, 30 patients requiring surgery (Fasanella Servat procedure) with bilateral ptosis will have one eye randomized to receive a bandage contact lens whereas the other eye will not after their surgery. Participants will have a random number assigned in order to anonymize data and protect patient identity. We will place a contact lens on both eyes and immediately take it off from one (this will be the sham lens eye). Randomization of the lens placement will be determined by a flip of a coin (heads – keep lens on right eye. Tails – keep lens on left eye). Investigator will randomly generate for each patient whether the contact lens will be kept on right or left eye, sham contact lens will be placed on other eye, placing it and immediately removing it. Therefore, the patient will not know which eye has a lens. Follow up will occur in one week after their surgery where the outcomes will be obtained through questionnaires. Upon 1 week follow up, the person administering the questionnaire is also blinded as they will not know which eye was randomized to have the lens placed. The primary outcome that will be obtained during the study is the patient's pain/discomfort. This will be obtained using the Eye Sensations Scale where the patient can select a box from None, Mild, Moderate, Severe, to Extreme. The secondary outcome that will be obtained is to determine if the patient has experienced blurry vision. This will be measured using one question from the Ocular Surface Disease Index (OSDI), with a scale from 0 (none of the time) to 4 (all of the time).

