### **Statistics and Analysis**

This randomized controlled trial will enroll consecutive patients and randomizing one eye to control treatment and the other eye to the experimental treatment. Assuming a mean pain score of 3.5 with standard deviation of 1.6 for control treatment, we need to enroll 30 patients and randomize one eye to control and one to experimental treatment to detect a mean difference of one score in pain with beta of 0.1 (90% power) and alpha of 0.05 (significance level of 0.05) if the null hypothesis of no difference in population means is true.

Baseline characteristics will be summarized as frequencies and relative frequencies for categorical data and mean and standard deviation for continuous data. Paired t-test will be used to compare the pain score between control and experimental eye and mean difference with 95% confidence interval will be reported as treatment effect. For categorical outcome measure, McNemar test will be used for comparison between control and experimental eye and proportions will be reported. A p-value of 0.05 will be set for statistical significance.

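### The lens eye is chosen by the investigator's coin flip, with no concealment, no timing relative to completion of both lids and no verifiable record described

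*Combined protocol and SAP*

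**What the plan says.** The whole allocation procedure is in the Methods section, under Design and Procedure. "Randomization of the lens placement will be determined by a flip of a coin", with heads meaning the right eye keeps the lens and tails the left. The same paragraph adds: "Investigator will randomly generate for each patient whether the contact lens will be kept on right or left eye". Each patient "will have one eye randomized to receive a bandage contact lens whereas the other eye will not after their surgery". A lens is put on each eye and one is removed at once as the sham, so the side must be known by the time of that removal. Nothing says whether the flip comes before, during or after the operation.

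Three other statements come near the subject without filling the gap:
- "Participants will have a random number assigned in order to anonymize data and protect patient identity". This number serves confidentiality and is not described as an allocation list.
- "the person administering the questionnaire is also blinded as they will not know which eye was randomized to have the lens placed". This is blinding of the outcome assessment at one week. It does not conceal the allocation from the person who makes it.
- The trial "will enroll consecutive patients and randomizing one eye to control treatment and the other eye to the experimental treatment" (Statistics and Analysis). This limits choice of patients, not choice of eye.

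No prepared list, independent allocator, envelope, witness or log is mentioned. The Statistics and Analysis and Ethics sections add nothing on how the side is allocated.

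**The concern.** In a fellow-eye trial the treatment effect is the mean difference between the two eyes of the same person. Any link between the allocation and the state of the eye therefore goes straight into the primary result. Two routes are open:

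1. **After the lids have been seen.** A flip can be repeated or set aside so that the lens goes to a particular eye.
2. **Before the operation ends.** If the flip is made by then, and if the allocating investigator is also the operator (an assumption), the lens side could be known while the lids are being sutured.

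No misconduct needs to be supposed. The Project Summary gives protection from suture irritation as the reason for the lens, and the Ethics section describes it as usual care for many clinicians. A clinician of that view has a well-meant reason to leave the lens on the eye that looks rougher. Lens eyes would then score worse than a fair allocation would make them, and a true benefit would be partly hidden. That moves the result towards the hypothesis in the Project Summary that the lens has no major impact. Since such a result is meant to support dropping the lens, its allocation should be open to checking.

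**Working it through.** **The plan's own figure.** Inputs from Statistics and Analysis: SD 1.6, difference 1, alpha 0.05, power 90%, paired t-test, 30 patients. Take 1.6 as the SD of the within-patient difference and a two-sided test. The noncentral t distribution then gives n = 29 for 90% power (90.1%), and 91.1% at n = 30. The planned number reproduces on that reading, and nothing about allocation would change it.

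The plan gives 1.6 for the control treatment, not for the difference. If it is the single-eye SD and r is the between-eye correlation, the SD of the difference is 1.6 × √(2(1 − r)). That equals 1.6 at r = 0.5 and 1.6 × √2 = 2.26 at r = 0. Both are used below.

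**Bias from steering (assumptions, not in the documents).** Suppose one eye would score g points worse than the other whatever the treatment. Under a fair flip, the lens-minus-control difference from this source is +g or −g with equal chance, so its mean is 0. If the lens goes to the worse eye regardless of the coin, it is always +g. With a fraction f of patients steered in this way:

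bias = f × g

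Here f counts patients steered regardless of the coin. Half of them would have had the lens on that eye anyway. If f counted only flips actually reversed, each would move the difference from −g to +g and the bias would be 2 × f × g.

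**Effect on the test.** The noncentrality is bias ÷ (SD of differences ÷ √30). With SD 1.6 the standard error is 1.6 ÷ √30 = 0.292, and the two-sided 5% critical value on 29 degrees of freedom is 2.045. For f = 20% and g = 1 the bias is 0.20 and the noncentrality 0.20 ÷ 0.292 = 0.68, giving a rejection probability of 10.2% when the lens has no effect. For power, the true one-point benefit is reduced to 1 − f × g. The SD is held fixed throughout.

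| g | SD of differences | f = 10% | f = 20% | f = 30% |
|---|---|---|---|---|
| 0.5: bias | – | 0.05 | 0.10 | 0.15 |
| 0.5: type I error | 1.6 | 5.3% | 6.3% | 7.9% |
| 1: bias | – | 0.10 | 0.20 | 0.30 |
| 1: type I error | 1.6 | 6.3% | 10.2% | 16.8% |
| 1: type I error | 2.26 | 5.6% | 7.5% | 10.8% |
| 1: power for a one-point benefit (91% with no steering) | 1.6 | 85% | 75% | 64% |

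The extra false rejections would mostly make the lens look harmful. The loss of power is the part that favours the trial's hypothesis.

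**The case against.** A fair coin is random and unpredictable, every patient receives both conditions, and enrolment is consecutive. The patient and the person giving the questionnaire are blinded. The protocol is very short, and silence is not proof that safeguards are absent. All of this stands, and it rules out several stronger readings that a reader might infer:

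- **That the allocation is unrecorded and unconcealed.** The documents do not say so. The lens side must be noted somewhere, because the paired analysis needs it and the questionnaire administrator does not know it. What is not described is a verifiable record of the flip made at allocation.
- **That the surgeon makes the flip.** The text says investigator and does not identify that person as the operator. The suturing route also needs a flip before the end of surgery, whereas the more natural reading is that the side is settled when one lens is removed. It is the weaker of the two routes.
- **That two conflicting methods are specified.** The two sentences can be read together: the investigator generates the side by flipping the coin. The wording is untidy rather than contradictory.
- **That an uneven right/left split would bias the result.** Each patient supplies both conditions, so the split matters only if side itself affects pain, and nothing in the documents suggests that.

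The sizes are also open to challenge. A one-point gap between eyes equals the trial's whole target difference, on a five-category scale. With half a point the effect on type I error is modest.

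None of this answers the repeat-or-override route. A coin is unpredictable before it is thrown, but its result can be discarded afterwards, and blinding at one week does not prevent that.

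**Conclusion.** The concern holds in this form: the plan leaves the choice of eye to a flip by the investigator and describes no concealment, no timing relative to completion of both lids, and no record by which the flip could be checked. The change should be made; the gap does not show that the allocation would in fact be biased, and the documents do not support a claim that it would.

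The likely direction, if steering occurred for the reason given above, is against the lens. Its size depends on f, g and the SD of differences, none of which the documents give for this purpose. Over the values shown, the bias runs from 0.05 to 0.30 points against a target of one point. Type I error runs from 5.3% to 16.8% with SD 1.6, and from 5.6% to 10.8% with SD 2.26 and a one-point gap. These figures are illustrations, not estimates. The procedural gap itself rests on the text alone and on no assumption.

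**What to change.** Replace the coin-flip wording in Methods with a single procedure:

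- A computer-generated right/left list for 30 patients, linked to the study number already assigned. Simple randomisation is enough: the paired comparison does not need equal numbers of right and left eyes, and blocks could make later allocations guessable.
- The list is prepared and held by existing personnel outside the operating team.
- Allocations are kept in numbered opaque sealed envelopes. Each is opened only after both lids are finished, which still precedes removal of the sham lens.
- The allocated eye is logged with date and time at opening.

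The cost is one generated list, 30 envelopes, a log sheet and one paragraph of protocol text. Sample size, visits and analysis are unchanged. The downside is minor preparation, which has to be done before the first case because the allocation cannot be verified afterwards.
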